9.3 Severity

Adverse events are first graded according to seriousness and then severity. The seriousness of an event is determined by the regulatory criteria in Section 9.6.

The Investigator will evaluate the severity of each AE. Adverse events will be graded as

Mild: Awareness of symptoms but easily tolerated

Moderate: Discomfort enough to interfere with but not prevent daily activity

Severe: Unable to perform usual activity

9.4 Relationship

The Investigator will judge the likelihood that the AE was related to the investigational product according to the following criteria

Not related: There is no temporal or causal relationship to the investigational product.

Related: There is a possible temporal or causal relationship to the investigational product.

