Planned efficacy analyses will include examination of changes in iron chelation. Analysis by TDT and NTDT stratification will depend on recruitment status. Descriptive summaries of serum ferritin at each time point in each study period will be completed. Change from baseline in serum ferritin will be assessed with a mixed model for repeated measures (MMRM) to assess changes within each treatment period and time. Categorical summaries will be presented for efficacy responders, i.e., the proportion of patients who achieve serum ferritin <800 mcg/L.

Pharmacokinetic parameters will be derived using model-independent methods (non-compartmental analysis: NCA) as implemented in Phoenix 7, WinNonlin (version 7.1) and will be based on DST-0509 and Jadenu plasma concentrations from patients in the PK Population.

Pharmacokinetic parameter estimates will be estimated for each treatment. Both single dose PK parameter estimates (following the first dose in a treatment sequence) and multiple dose pharmacokinetic parameter estimates will be completed to characterize DST-0509 and Jadenu. Other pharmacokinetic parameters may be defined as data are explored in the Phase 2 study.

Safety analyses will be performed on the Safety Population. AEs will be coded using the Medical Dictionary for Regulatory Activities (MedDRA) dictionary (version 20.1). Incidences (number and percent) of Treatment Emergent AEs (TEAEs), those events that started after dosing or worsened in severity after dosing, will be presented by treatment group. Incidences of TEAEs will also be presented by maximum severity and relationship to study medication. Laboratory data and vital sign information will be summarized by treatment group as summary statistics for value and change from Baseline at each individual time point. Summary statistics will include n, mean, median, standard deviation (SD), minimum, and maximum. Details for the additional safety endpoints will be provided in the SAP.

SAMPLE SIZE DETERMINATION:

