3.1 Overall Study Design

This is a multi-center, open-label, two-period cross-over, patient-pilot study comparing DST-0509 to Exjade or Jadenu administered orally once daily (QD) for 28-days in each period, with a 7-day washout before study entry and between treatment periods (see Table 6-1). Patients will be randomized to one of two treatment sequences: DST-0509→Exjade/Jadenu or Exjade/Jadenu→DST-0509 (with subjects who were taking Exjade prior to study start receiving Exjade and those taking Jadenu at study start receiving Jadenu). This study is designed to assess the safety, tolerability, evidence of iron chelating activity, and PK profile of DST-0509 compared to Jadenu or Exjade in inadequately responding patients. Inadequate response to standard chelation therapy is defined from the medical literature [6,7].

Up to 36 patients will be randomized 1:1 into one of two treatment sequences (study arms), of which up to 100% may be on Jadenu or Exjade at study entry, or a mix of the two. The planned randomization will assign up to 18 patients in each of two sequences: Sequence A: DST-0509 crossed to Exjade or Jadenu; Sequence B: Jadenu or Exjade crossed to DST-0509. The comparator treatment will be the patient's current chelation treatment. At the end of the study, patients previously on Jadenu or Exjade will revert to receiving their pre-study medication and dose following a 7-day washout period. A sufficient number of patients will be enrolled so there will be no need to replace study drop-outs. Study duration is approximately 14 weeks for each patient. A Study Flow Diagram is presented after this Synopsis (see Figure 3-1).

Figure 3-1: Study Flow Diagram

Treatment A (28 days) = DST-0509
Treatment B (28 days) = Jadenu/Exjade¹

*Up to 36 patients are planned.

- Subjects taking Exjade prior to study start will receive Exjade (treatment B) in the assigned Period 1 or cross-over Period 2. Those patients taking Jadenu prior to study start will receive Jadenu (treatment B) in the assigned Period 1 or cross-over Period 2. Dosing will be at equivalent (mg for mg) doses of DST-0509 for Jadenu. If crossing over from Exjade to DST-0509, or vice versa, the dose will be scaled to 28 mg/40 mg (DST-0509/Exjade).
- For all patients entering the trial, a 7-day washout is required.

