7.6 Washout

There will be a 7-day washout period before initial treatment with study drug, a second 7-day washout after the crossover and before treatment with the second study drug, and a third 7-day washout period at the end of the study on Day 63.

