8.5.3 Safety Analyses

Adverse Events

Adverse experiences will be coded using Medical Dictionary for Regulatory Activities (MedDRA, version 20.0 or higher) and summarized by System Organ Class (SOC) and Preferred Term for each treatment group. All AEs will be captured after the first dose through the final visit (Visit 11) or the ET visit.

Adverse events will be summarized by presenting:

- the number and percentage of patients experiencing any AE
- the number and percentage of patients experiencing any AE grouped by SOC
- the number and percentage of patients experiencing any SAE
- the number and percentage of patients experiencing any AE associated with study discontinuation.

Gastrointestinal Adverse Events of Special Interest (GI AESI)

In addition, safety will also include assessing adverse events of special interest (AESI) including selected gastrointestinal AEs of diarrhea, constipation, nausea, vomiting, and abdominal pain.

Other Safety and Tolerability Parameters

At each clinic visit, treatment exposure will be estimated with compliance rates based on patient diary cards and pill counts, and tolerability will be assessed by general enquiry and specific iron chelation tolerability questions as well as by patient diaries concerning tolerability. Study patients will receive a diary to record gastrointestinal (GI) adverse events (AEs) of special interest (AESI) during the course of the study. Patients will be given the Bristol Stool Chart with diary and instructed on its use to help them characterize the nature of the bowel movements. All AE's will be monitored throughout the trial.

Patient safety will be monitored per clinical standard of care including routine laboratory monitoring. This will include monthly CBC, chemistry panel, and urinalysis assessments. Urine will be collected to measure protein: creatinine ratio and serum CRP will be assessed.

Compliance

Patients will be responsible for supplying their own Jadenu or Exjade during the study. Pill counts will be performed at each visit in order to characterize patient compliance (calculated as % doses taken per protocol). Additional measures of compliance will include Investigator enquiry into patient prescription refill records if available, satisfaction with iron chelation therapy (SICT) questionnaire [ref 8; [Appendix D](#)] and use of patient diaries.

Dose reductions

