9 ADVERSE EVENT MONITORING

9.1 Definition

An AE is defined as any untoward medical occurrence in a patient or clinical investigation following the patient's first dose of investigational product that does not necessarily have a causal relationship with this treatment. An AE can be any unfavorable or unintended sign (including an abnormal finding), symptom, or disease temporally associated with the use of a medicinal (investigational) product, whether or not related to the medicinal (investigational) product.

This includes any occurrence that is new in onset or aggravated in severity or frequency from the baseline condition (including the physical examination), or abnormal results of diagnostic procedures (including laboratory test abnormalities).

Events should be considered AEs if they:

- result in discontinuation from the study,
- require treatment or any other therapeutic intervention,
- require further diagnostic evaluation (excluding a repetition of the same procedure to confirm the abnormality),
- are associated with clinical signs or symptoms judged by the Investigator to have a significant clinical impact.

Clinically Significant Laboratory Changes: It is the Investigator's responsibility to review the results of all laboratory tests as they become available. For each abnormal result, the Investigator needs to ascertain whether the abnormality presents a clinically significant change from baseline. If the change is due to the expected course of the patient's underlying disease (e.g., elevated cholesterol in a study of dyslipidemia), it is not considered an adverse event unless the abnormality is more severe than expected. A laboratory test may be confirmed by repeat testing or other diagnostic tests before being considered an adverse event. If the laboratory abnormality is a significant change from baseline for the patient, then it should be considered an adverse event.

An Adverse Event is not:

- A surgical procedure
- A situation where an untoward event did not occur, (e.g. a social hospitalization)
- The disease being studied, unless progression is more severe than anticipated
- Lack of efficacy
- Baseline conditions that have not worsened in severity or frequency
- Clinically significant abnormal laboratory findings or test results related to the disease being studied (unless more severe than expected)

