9.7 Unexpected Adverse Event

As defined by 21 CFR 312.32 (a), an unexpected adverse drug experience is:

"An adverse event or suspected adverse reaction is considered "unexpected" if it is not listed in the Investigator's Brochure or is not listed at the specificity or severity that has been observed; or, if an Investigator's Brochure is not required or available, is not consistent with the risk information described in the general investigational plan or elsewhere in the current application, as amended. For example, under this definition, hepatic necrosis would be unexpected (by virtue of greater severity) if the Investigator's Brochure referred only to elevated hepatic enzymes or hepatitis. Similarly, cerebral thromboembolism and cerebral vasculitis would be unexpected (by virtue of greater specificity) if the Investigator's Brochure listed only cerebral vascular accidents. "Unexpected," as used in this definition, also refers to adverse events or suspected adverse reactions that are mentioned in the Investigator's

Brochure as occurring with a class of drugs or as anticipated from the pharmacological properties of the drug but are not specifically mentioned as occurring with the particular drug under investigation.”

The study Sponsor will expedite reporting to Center for Biologics Evaluation and Research (CBER) all serious unexpected suspected adverse reactions (SUSARs) as defined in the Investigator’s Brochure (IB) [9]: initial reporting by the Sponsor for nonfatal or non-life-threatening SUSARs must be submitted to CBER as soon as possible but no later than within 15 calendar days following the Sponsor’s initial receipt of the information, and for fatal or life-threatening SUSARs, initial reports must be submitted no later than 7 calendar days following the Sponsor’s initial receipt of the information. Any relevant additional information obtained by the Sponsor that pertains to a previously submitted IND Safety Report must be submitted as a Follow-up IND Safety Report without delay as soon as the information is available but no later than 15 calendar days after the Sponsor receives the information.

Such expedited reports will comply with the applicable regulatory requirements and with the FDA’s Guidance for Industry and Investigators Safety Reporting Requirements for INDs and BA/BE Studies (21 CFR 312.32).

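### Section 9.4 lets timing alone make an adverse event Related, so the relationship item says little about causation for events during daily dosing

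*Protocol*

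**What the plan says.** Section 9.4 has the investigator judge how likely it is that an AE was related, using two listed criteria:

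- "Related: There is a possible temporal or causal relationship to the investigational product"
- "Not related: There is no temporal or causal relationship to the investigational product"

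Section 9.1 defines an AE as an occurrence after the first dose. It adds that an AE can be any unfavourable sign, symptom or disease "temporally associated with the use of a medicinal (investigational) product, whether or not related to the medicinal (investigational) product".

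Treatment is "administered orally once daily (QD) for 28-days in each period". On the collection window, section 8.5.3 states: "All AEs will be captured after the first dose through the final visit (Visit 11) or the ET visit". Section 9.2 requires the relationship to be entered on the case report form for every AE. The Synopsis (Statistical Analyses) plans to use it: "Incidences of TEAEs will also be presented by maximum severity and relationship to study medication".

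**The concern.** A causality item should separate events the drug may have caused from events that merely happened while the patient was taking it. Section 9.4 does not do this. Either limb is enough for Related, and both must be absent for Not related. A patient injured in an accident on a dosing day has an event with an obvious other cause and a possible temporal relationship, so the rule as written makes it Related.

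Safety and tolerability are the primary endpoints (section 8.1), and the relationship table is meant to help interpret them. If investigators follow the rule, the table adds little to the all-event table. If they use clinical sense instead, each departs from the rule in a personal way, in an open-label study where the current drug is known. A later analysis plan cannot recover a causal judgement that was never collected.

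**Working it through.** The plan gives no figure for relatedness. Its only design figure is the chance of seeing diarrhea events (section 8.1). With a true rate of 12% and N = 30, 1 − 0.88^30 = 0.978, which matches the stated 98%. That figure counts events regardless of relationship, so nothing below changes it.

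**1. Logic of the two categories.** Write T for a possible temporal relationship and C for a causal one. Related is T or C; Not related is neither. If T holds for a set of events, all of them are Related whatever the share with C. For assumed causal shares of 10%, 30% and 50%, the rule labels 100% Related each time. A definition that required causation would give 10%, 30% and 50%.

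**2. Sections 9.1 and 9.4 side by side.** In 9.1, temporal association belongs to being an AE and leaves relatedness open. In 9.4, the same attribute settles relatedness.

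**3. Days on which T plainly holds** (inputs: sections 3.1, 7.6, 8.5.3 and Table 6-1).

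- Capture window for a completer: Day 1 to Day 70, 70 days.
- Dosing days: 1–28 and 36–63, so 28 + 28 = 56, and 56/70 = 80%.
- Off-drug days: 29–35 and 64–70, so 14, and 14/70 = 20%.

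**4. Off-drug days.** The protocol sets no period after a dose within which timing counts. Section 1.1 gives a mean half-life of 8–16 hours. Seven days is 168 hours, so 168/16 = 10.5 to 168/8 = 21 half-lives, and at most 0.5^10.5 ≈ 0.07% of the drug remains. An investigator could reasonably find no temporal relationship late in a washout.

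**5. Which product is assessed.** Section 9.4 refers to the investigational product, which section 5.1 identifies as DST-0509. Yet sections 6.3.1 and 6.4.1 dispense investigational product to all patients at the start of both periods, and the Synopsis table refers to study medication. Planned patient-days are 36 × 70 = 2,520. If only DST-0509 counts, they divide as follows:

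| Patient-days | Calculation | Share |
|---|---|---|
| On DST-0509 | 36 × 28 = 1,008 | 40% |
| Before any DST-0509 (Sequence B, Days 1–35) | 18 × 35 = 630 | 25% |
| After the DST-0509 period (Sequence A Days 29–70; Sequence B Days 64–70) | 18 × 42 + 18 × 7 = 882 | 35% |

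On this reading, no temporal relationship is possible on 25% of patient-days. Events during DST-0509 dosing default to Related, and Sequence B comparator events default to Not related. Since treatment-emergent events are presented by treatment group, the wording alone could then produce an apparent difference between the drugs.

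**The case against.** The strongest reply is that section 9.4 asks for a judgement of likelihood, so the two lines are guidance and not a timestamp test. This does not cure the wording, because the judgement is to be made by those two criteria, and under them a likely alternative cause does not make an event Not related.

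A second reply concerns importance, and much of it stands. The AE summaries listed in section 8.5.3 do not include relationship; it appears only in the Synopsis as a further presentation. The sample size rests on diarrhea AEs of any cause. In a randomized crossover, attribution rests mainly on comparing incidence between treatments, which section 9.4 does not touch.

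Two stronger readings are tempting, and the documents support neither.

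- *Every recorded AE must be Related.* A reader might infer this by treating any event within 7 days of a dose as temporally linked. The protocol has no such rule, 20% of the window is off drug, and section 9.5 foresees AEs when the patient is not on study drug. The DST-0509-only reading also leaves Not related open for Sequence B Period 1.
- *Expedited reporting is swamped.* A reader might infer that every unexpected serious event becomes a suspected reaction. But sites report SAEs whether or not they are judged related (section 9.8.1), and section 9.7 ties the sponsor's expedited reports to the Investigator's Brochure and 21 CFR 312.32 without citing 9.4. The label would matter there only if the sponsor adopted it as its own causality decision, which the protocol does not say.

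What remains is narrower: the label is a minimum item on each SAE report (section 9.8.1), and SAEs learned of after the final visit are submitted when believed possibly related (section 9.6).

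**Conclusion.** The concern holds in a limited form. As written, section 9.4 labels events during daily dosing Related whatever their cause, and it conflicts with section 9.1's separation of timing from relatedness. If the investigational product covers both treatments, this affects 56 of 70 capture days (80%) for a patient who completes as scheduled. If it means DST-0509 only, the rule binds plainly on 28 of 70 days (40%), and elsewhere the label tends to follow sequence and period. Either way, the relationship table says little about causation.

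These shares are of days, not events. They assume 18 patients per sequence and no early termination. The protocol gives no basis for predicting the share of AEs that would be recorded Not related. No sample size, power or significance level changes. The correction is worth making before data are collected, because the analysis cannot repair it afterwards.

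**What to change.** Amend section 9.4 as follows:

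- **Related:** on the evidence, there is a reasonable possibility that the product caused the event. Timing counts as supporting evidence but is not sufficient alone.
- **Not related:** there is no such reasonable possibility. Make this the exact complement of Related. Do not add a separate limb for cases where another cause is more likely, because an event could then meet both definitions.
- **Product assessed:** state that relationship is judged to the treatment of the current or most recent period (DST-0509 or Jadenu/Exjade), and use one term for it in 9.1, 9.4 and the Synopsis.
- **Forms:** carry the same wording on the AE and SAE forms.

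The cost is protocol wording and form-completion guidance. No extra data are needed, and no clinical-management rule changes.

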9.5 Action Taken and Outcome

The Action Taken with investigational product for every AE will be reported as either: Dose Not Changed, Dose Reduced, Dose Interrupted, Dose Withdrawn or Not Applicable if patient is not taking the study drug at the time of the adverse event. The outcome of each AE will be entered as either: Recovered/Resolved, Recovered/Resolved with Sequelae, Not Recovered/Not Resolved, Fatal, or Unknown.

9.6 Adverse Event Follow-up

Investigators should follow AEs until the event has resolved, the condition has stabilized, is well characterized, or referred for appropriate medical management, whichever comes first. Events and follow-up information occurring after the last visit should be recorded in the source documentation. Investigators are not obliged to solicit adverse events after a patient's final visit; however, if an Investigator learns of an Serious AE (SAE) that is believed to be possibly related to the investigational product, an SAE Report Form should be submitted.

9.7 Unexpected Adverse Event

As defined by 21 CFR 312.32 (a), an unexpected adverse drug experience is:

"An adverse event or suspected adverse reaction is considered "unexpected" if it is not listed in the Investigator's Brochure or is not listed at the specificity or severity that has been observed; or, if an Investigator's Brochure is not required or available, is not consistent with the risk information described in the general investigational plan or elsewhere in the current application, as amended. For example, under this definition, hepatic necrosis would be unexpected (by virtue of greater severity) if the Investigator's Brochure referred only to elevated hepatic enzymes or hepatitis. Similarly, cerebral thromboembolism and cerebral vasculitis would be unexpected (by virtue of greater specificity) if the Investigator's Brochure listed only cerebral vascular accidents. "Unexpected," as used in this definition, also refers to adverse events or suspected adverse reactions that are mentioned in the Investigator's

Brochure as occurring with a class of drugs or as anticipated from the pharmacological properties of the drug but are not specifically mentioned as occurring with the particular drug under investigation.”

The study Sponsor will expedite reporting to Center for Biologics Evaluation and Research (CBER) all serious unexpected suspected adverse reactions (SUSARs) as defined in the Investigator’s Brochure (IB) [9]: initial reporting by the Sponsor for nonfatal or non-life-threatening SUSARs must be submitted to CBER as soon as possible but no later than within 15 calendar days following the Sponsor’s initial receipt of the information, and for fatal or life-threatening SUSARs, initial reports must be submitted no later than 7 calendar days following the Sponsor’s initial receipt of the information. Any relevant additional information obtained by the Sponsor that pertains to a previously submitted IND Safety Report must be submitted as a Follow-up IND Safety Report without delay as soon as the information is available but no later than 15 calendar days after the Sponsor receives the information.

Such expedited reports will comply with the applicable regulatory requirements and with the FDA’s Guidance for Industry and Investigators Safety Reporting Requirements for INDs and BA/BE Studies (21 CFR 312.32).

